5.8.3. Management of cerebral edema

Due to the immunologic nature of anti-PD-1 and GITR therapy, cerebral edema could theoretically result as a consequence of immune infiltration of the brain. In addition, SRS is expected to elicit cerebral edema. Symptoms related to cerebral edema may include headache or neurologic deficit that is either new or worsened. Participants with any signs or symptoms of cerebral edema in the investigator's judgment should be treated as clinically appropriate including initiation or increased dosing of systemic corticosteroids, osmotic diuretics, and/or surgical decompression. Subsequent study drug treatment should be immediately interrupted if significant clinical symptoms attributable to cerebral edema in the investigator's judgment develop. Treatment with additional study drug may only be re-initiated if clinically significant symptoms attributable to cerebral edema have stabilized or significantly resolved in the investigator's judgment.

Participants who develop grade 4 cerebral edema (CTCAE v5) attributable to study drug administration should not receive further study drug. Grade 4 cerebral edema is defined as life-threatening or requiring urgent intervention. For this study, urgent intervention refers to urgent/emergent intensive care unit admission, intubation for hyperventilation, administration of hypertonic or hyperosmotic agents, and/or urgent/emergent surgical decompression.

5.9 Disposal of Investigational Products

Study drug containers should not be destroyed until permitted by the Sponsor. Any unused study drug will be destroyed at the study site, per SOP.

5.10 Surgical Resection (Cohort B only)

For subjects enrolled onto cohort B, surgical resection for maximal safe tumor resection will be performed according to standard clinical practice. There is no aspect of this surgery that is different from standard practice.

5.11 Radiation Planning and Delivery (Cohort A; Cohort B, sub-arm #1 only)

Treatment will consist of 24 Gy delivered in 3 fractions over 3 consecutive business days. Subjects may receive 3 fractions every other day (non-consecutively) for logistical reasons relating to COVID-19. Therapy will be delivered according to standard guidelines of brain

directed SRS using the Cyberknife system or other linear accelerators commissioned for SRS. Patients will be simulated as per standard procedures with a CT and MRI scan in the treatment position with the patient immobilized in a thermoplastic mask. CT scan slice thickness will be 1.5mm. MRI images obtained at the time of simulation or diagnostic images will be fused as per department guidelines by a qualified physicist or dosimetrist and alignment confirmed by the treating radiation oncologist. For daily treatments patients will be immobilized in the custom thermoplastic masks created at simulation and undergo standard image guidance per routine care (6D skull tracking for Cyberknife treatments and volumetric cone beam CT for LINAC based treatments).

The gross tumor volume (GTV) will be defined as the enhancing tumor on the T1 post Gadolinium MRI scan. No expansion to a clinical target volume (CTV) will be applied (ie GTV=CTV). A planning target volume (PTV) expansion to account for setup uncertainty will be 1-2mm. Normal tissues to be contoured include the brainstem, optic nerves, optic chiasm, eyes, lens, cochlea. All radiation plans will undergo standard peer review prior to initiation of therapy. Target coverage and dose constraints are listed below in **Table 7**:

Table 7. Radiation Guidelines

Dose Metric	Per Protocol	Variation excepted
PTV_2400	Greater than or equal to 95% of the PTV should receive greater than or equal to 22.8 Gy. Max dose less than 28.8 Gy.	Greater than or equal to 90% of the PTV should receive greater than or equal to 22.8 Gy. Max dose less than 28.8 Gy.
Brainstem	Maximum dose from current plan (0.03cc) <23 Gy Maximum dose from combined plans (0.03cc)< 68Gy	
Optic Chiasm	Maximum dose from current plan (0.03cc) <17 Gy Maximum dose from combined plans (0.03cc)< 63Gy	
Optic Nerve	Maximum dose from current plan (0.03cc) <17 Gy Maximum dose from combined plans (0.03cc)< 63Gy	
Eyes	Maximum dose from current plan (0.03cc) <14 Gy	

	Maximum dose from combined plans (0.03cc) < 58Gy	
Cochlea	Maximum dose from current plan (0.03cc) < 17 Gy Maximum dose from combined plans (0.03cc) < 53Gy Mean dose from combined plans (0.03cc) < 50Gy	Maximum dose from current plan (0.03cc) < 25 Gy Maximum dose from combined plans (0.03cc) < 60Gy Mean dose from combined plans (0.03cc) < 55Gy

6 STUDY PROCEDURES

Screening assessments are to be conducted within 14 days prior to initiating protocol therapy unless otherwise specified. Screening assessments occurring prior to initiating study treatment do not need to be repeated on Cycle 1 Day 1 unless otherwise specified. Screening laboratory assessments must be done within 7 days prior to initiating protocol therapy.

For women of childbearing potential, as defined in the eligibility criteria, a pregnancy test must be completed within 7 days prior to initiating protocol therapy. If a urine pregnancy test is positive or cannot be confirmed as negative, a serum pregnancy test will be required.

The schedule of study procedures for the screening and intervention phases of the study for Cohort A is displayed in **Table 8** and for Cohort B in **Table 9**. The schedule of procedures for the follow-up phase of the study for both cohorts is displayed in **Table 10**.

Table 8: COHORT A (N=16): Schedule of Study Procedures, SCREENING AND INTERVENTION

Study Week	Screen	W1	W1	W2	W3	W5	W7	Q 4 weeks		Q 8 weeks	EOT§
								Cycle X	Cycle X	Cycle X (pre-odd cycles only)	
Cycle # (28-day cycles)		Cycle 1	Cycle 1	Cycle 1	Cycle 1	Cycle 2	Cycle 2	Cycle X	Cycle X	Cycle X (pre-odd cycles only)	
Day (and window)	-14 to 1	1	5 ± 2	8	15 ± 2	1 ± 2	15 ± 2	1 ± 2	15 ± 2	1 ± 2	
Informed Consent	X										
Review Inclusion/Exclusion Criteria (Section 4)	X										
Karnofsky Performance Status (Section 7)	X	X			X	X	X	X	X		X
Demographics/Medical History (Section 7)	X										
Physical Assessment (targeted after screening visit) (Section 7)	X	X			X	X	X	X	X	X	X
Vital Signs: BP, HR, RR (Section 7)	X	X			X	X	X	X	X		X
ECG (Section 7)											
Weight (Section 7)	X	X				X		X			X
Height (Section 7)	X										
Pregnancy Test (Section 7; within 7d of first dose of study drug)	X							X			X
Concomitant Medications (Section 7)	X	X			X	X	X	X	X		X

Study Week	Screen	W1	W1	W2	W3	W5	W7	Q 4 weeks		Q 8 weeks	EOT§
Cycle # (28-day cycles)		Cycle 1	Cycle 1	Cycle 1	Cycle 1	Cycle 2	Cycle 2	Cycle X	Cycle X	Cycle X (pre-odd cycles only)	
Day (and window)	-14 to 1	1	5 ± 2	8	15 ± 2	1 ± 2	15 ± 2	1 ± 2	15 ± 2	1 ± 2	
Clinical Laboratory Evaluation – non-endocrine (CBC, CMP, Mag, Phos, LDH) (Section 7; within 7d of first dose of study drug; Labs can be collected up to -3 days prior to treatment).	X	X			X	X	X	X	X		X
HBV/HCV screening (Section 7)	X										
Clinical laboratory Evaluation – endocrine (TSH, T4) (Section 7) Labs can be collected up to -3 days prior to treatment.	X									X	X
Urinalysis (Section 7)	X										X
Blood collected for INCAGN01876 PK (Section 7)		X***		X	X		X	X***†	X***†		
Blood collected for INCAGN01876 ADA (Section 7)		X			X		X		X		
Blood collected for correlatives (Section 7)		X				X				X	X

Study Week	Screen	W1	W1	W2	W3	W5	W7	Q 4 weeks		Q 8 weeks	EOT§
Cycle # (28-day cycles)		Cycle 1	Cycle 1	Cycle 1	Cycle 1	Cycle 2	Cycle 2	Cycle X	Cycle X	Cycle X (pre-odd cycles only)	
Day (and window)	-14 to 1	1	5 ± 2	8	15 ± 2	1 ± 2	15 ± 2	1 ± 2	15 ± 2	1 ± 2	
Adverse Event / Unanticipated Problems Assessment (Section 7)	X	X			X	X	X	X	X		X
INCMGA00012 Administration (Section 5)		X				X		X			
INCAGN01876 Administration (Section 5)		X			X	X		X	X		
MRI brain (tumor assessment by mRANO criteria) (Section 7)	X									X*	X††
SRS planning (Section 5)	X										
SRS delivery** (Section 5)			X								

* MRI scan should be performed within 7 days prior to the cycle start (and ideally within 3 days prior). Adjustments to this 7 day window are allowable per the treating physician’s discretion; however restaging scans MUST BE performed and reviewed before the subsequent cycle’s dose may be initiated

**SRS delivery: Total 24 Gy delivered over 3 consecutive days (8 Gy per day). Subjects may receive 3 fractions every other day (non-consecutively) for logistical reasons relating to COVID-19. Must start between 3 and 7 days after first dose of study drugs

*** PK samples for INCAGN01876 collected pre-dose and at end of infusion on Cycle 1 Day 1 and Cycle 3 Day 15. All other PK draws for INCAGN01876 are pre-dose.

† After the first 2 cycles, PK samples for INCAGN01876 are drawn only on Cycle 3 Day 15, Cycle 4 Day 1, Cycle 4 Day 15, and then only on day 15 of each cycle starting with Cycle 5

†† MRI and mRANO assessment at EOT are only necessary if this has not already been performed within 28 days of the EOT visit

§ EOT visit occurs within 14 days from when the subject is taken off study.

Table 9: COHORT B (N=16): Schedule of Study Procedures, SCREENING AND INTERVENTION

Study Week	Screen	Neo-adjutant week		Peri-op weeks		W1	W2	W3	W5	W7	Q 4 weeks		Q 8 weeks	EOT§
		Pre-Op	Post-Op	Cycle 1	Cycle 1	Cycle 2	Cycle 2	Cycle X	Cycle X	Cycle X (pre-odd cycles only)				
Cycle # (28-day cycles)		Neo- adjutant cycle												
Day (and window)	-14 to 1	1	5 ± 2	Within 1 day of surgery	Up to 3 days from surgery	1 ± 2	8	15 ± 2	1 ± 2	15 ± 2	1 ± 2	15 ± 2	1 ± 2	
Informed Consent	X													
Review Inclusion /Exclusion Criteria (Section 4)	X													
Karnofsky Performance Status (Section 7)	X	X				X		X	X	X	X	X		X
Demographics/ Medical History (Section 7)	X													
Physical Assessment(targeted after screening (Section 7)	X	X				X		X	X	X	X	X	X	X

Study Week	Screen	Neo-adjvant week		Peri-op weeks		W1	W2	W3	W5	W7	Q 4 weeks		Q 8 weeks	EOT§
		Neo-adjvant cycle		Pre-Op	Post-Op	Cycle 1	Cycle 1	Cycle 1	Cycle 2	Cycle 2	Cycle X	Cycle X	Cycle X (pre-odd cycles only)	
Day (and window)	-14 to 1	1	5 ± 2	Within 1 day of surgery	Up to 3 days from surgery	1 ± 2	8	15 ± 2	1 ± 2	15 ± 2	1 ± 2	15 ± 2	1 ± 2	
Vital Signs: BP, HR, RR (Section 7)	X	X		X		X		X	X	X	X	X		X
ECG (Section 7)	X													
Weight (Section 7)	X	X				X			X		X			X
Height (Section 7)	X													
Pregnancy Test (Section 7; within 7d of first dose of study drug)	X										X			X
Concomitant Medications (Section 7)	X	X		X		X		X	X	X	X	X		X
Clinical Laboratory Evaluation – non-endocrine (CBC, CMP, Mag, Phos, LDH) (Section 7; within 7d of first dose of study drug; Labs can be collected up to -3 days prior to treatment)	X	X			X	X		X	X	X	X	X		X

Study Week	Screen	Neo-adjvant week		Peri-op weeks		W1	W2	W3	W5	W7	Q 4 weeks		Q 8 weeks	EOT§
		Neo-adjvant cycle		Pre-Op	Post-Op	Cycle 1	Cycle 1	Cycle 1	Cycle 2	Cycle 2	Cycle X	Cycle X	Cycle X (pre-odd cycles only)	
Day (and window)	-14 to 1	1	5 ± 2	Within 1 day of surgery	Up to 3 days from surgery	1 ± 2	8	15 ± 2	1 ± 2	15 ± 2	1 ± 2	15 ± 2	1 ± 2	
Clinical laboratory Evaluation – endocrine (TSH, T4) (Section 7) Labs can be collected up to -3 days prior to treatment.	X					X							X	X
Urinalysis (Section 7)	X													X
HBV/HCV screening (Section 7)	X													
Blood collected for INCAGN01876 PK (Section 7)						X***	X	X		X	X†	X***†		
Blood collected for INCAGN01876 ADA (Section 7)						X		X		X		X		
Blood collected for correlatives (Section 7)		X				X			X				X	X

Study Week	Screen	Neo-adjvant week		Peri-op weeks		W1	W2	W3	W5	W7	Q 4 weeks		Q 8 weeks	EOT§
		Neo-adjvant cycle		Pre-Op	Post-Op	Cycle 1	Cycle 1	Cycle 1	Cycle 2	Cycle 2	Cycle X	Cycle X	Cycle X (pre-odd cycles only)	
Day (and window)	-14 to 1	1	5 ± 2	Within 1 day of surgery	Up to 3 days from surgery	1 ± 2	8	15 ± 2	1 ± 2	15 ± 2	1 ± 2	15 ± 2	1 ± 2	
Adverse Event / Unanticipated Problems Assessment (Section 7)	X	X		X	X	X		X	X	X	X	X		X
INCMGA00012 Administration (Section 5)		X††				X			X		X			
INCAGN01876 Administration (Section 5)		X††				X		X	X	X	X	X		
MRI brain (tumor assessment by mRANO criteria) (Section 7)	X												X*	X†††
SRS planning** (Section 5)	X													
SRS delivery** (Section 5)			X											
Surgical Resection; tissue for correlatives (Section 7)				X										

* MRI scan should be performed within 7 days prior to the cycle start (and ideally within 3 days prior). Adjustments to this 7-day window are allowable per the treating physician’s discretion; however restaging scans MUST BE performed and reviewed before the subsequent cycle’s dose may be initiated

**SRS delivery: Total 24 Gy delivered over 3 consecutive days (8 Gy per day). Subjects may receive 3 fractions every other day (non-consecutively) for logistical reasons relating to COVID-19. Must start between 3 and 7 days after first dose of study drugs

*** PK samples for INCAGN01876 collected pre-dose and at end of infusion on Cycle 1 Day 1 and Cycle 3 Day 15. All other PK draws for INCAGN01876 are pre-dose.

† After the first 2 cycles, PK samples for INCAGN01876 are drawn only on Cycle 3 Day 15, Cycle 4 Day 1, Cycle 4 Day 15, and then only on day 15 of each cycle starting with Cycle 5

†† For the neoadjuvant dose(s) of study drugs INCMGA00012 and INCAGN01876, the subject will be assigned to receive the combination of INCMGA00012 and INCAGN01876, or the combination of INCMGA00012 and INCAGN01876 plus SRS. After surgery ALL subjects will resume the combination of both INCMGA00012 and INCAGN01876

††† MRI and mRANO assessment at EOT are only necessary if this has not already been performed within 28 days of the EOT visit
§ EOT visit occurs within 14 days from when the subject is taken off study

Table 10: Schedule of study procedures, FOLLOW-UP			
Procedure	Safety visit	Safety follow-up	Disease Status and Survival
	30 d after EOT (+/- 7 d)	12 W (+/-14 d) after EOT	Q12W after EOT (+/- 14d)
Karnofsky Performance Status (Section 7)	X		
Targeted Physical Assessment (Section 7)	X		
Vital Signs: BP, HR, RR, weight (Section 7)	X		
Prior/Concomitant Medications (Section 7)	X	X	
Clinical Laboratory Evaluation (CBC, CMP, Mag, Phos, LDH) (Section 7)	X		
Urinalysis (Section 7)	X		
Clinical laboratory Evaluation – endocrine (TSH, T4) (Section 7)	X		
Urine Pregnancy Test (Section 7)	X		
Adverse Event / Unanticipated Problems Assessment (Section 7)	X	X*	
MRI brain (tumor assessment) (Section 7)			X
Subject Vital Status (Collection of survival information every 3 months until death, lost to follow-up, or withdrawal of study consent)			X

* Only immune related Adverse Events are to be collected at the 12-week safety follow- up timepoint (see sections 1.3.1.3 and 1.3.2.3).

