and described in detail in **Appendix 1** with specific application to this protocol. These recommendations include management of the toxicity itself, as well as guidance for dose interruptions/delays of the investigational agents. There are no dose reductions or dose escalations permitted for either investigational agent.

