7.3 Vital Signs

Height will be assessed at screening only. Weight will be assessed according to the Study Schedule (**Tables 8 and 9**) and as clinically indicated at any other time.

Vital signs (BP, pulse, temperature, and respiratory rate) will be evaluated according to the assessment schedules (**Table 8 and Table 9**). Any changes in vital signs should be recorded as an AE, if applicable. Body temperature: Body temperature will be measured in degrees Celsius at the times indicated in the Study Schedule (**Table 8 and Table 9**).

On infusion days, subjects will be monitored during and after infusion of each investigational product(s) as presented in the bulleted list below. Supine BP will be measured using a semi-automatic BP recording device with an appropriate cuff size, after the subject has rested for at

least 5-10 minutes. BP and pulse will be collected from subjects before, during, and after each infusion at the following times (based on a 60-minute infusion):

- Prior to the beginning of the infusion (measured once from approximately 30 minutes before up to 0 minutes [ie, the beginning of the infusion])
- Approximately 30 minutes during 60-minute infusions (halfway through infusion). Vitals should be obtained at approximately 15 minutes during subsequent 30-minute infusions (halfway through infusion).
- At the end of the infusion (approximately 60 or 30 minutes \pm 5 minutes)
- A 1-hour observation period is recommended after the INCMGA00012 infusion prior to beginning the INCAGN01876 infusion.

7.4 *Electrocardiogram (ECG)*

A 12-lead electrocardiogram will be performed at screening only.

7.5 *Clinical Laboratory Evaluations*

Blood sampling will be performed for the following laboratory evaluations (**Table 12**) according to the schedule outlined in **Table 8 and Table 9**:

- Hematology
- Chemistry and Liver Function
- Additional electrolytes
- Endocrine
- Hepatitis screening
- Urinalysis

Category	Tests
Hematology	RBC, hemoglobin, hematocrit, platelet count, WBC with differential
Chemistry and Liver function tests (comprehensive metabolic panel)	Basic metabolic panel, LDH, AST, ALT, total Bilirubin (with direct and indirect components), alkaline phosphatase
Additional electrolytes	Magnesium, phosphorus
Endocrine	TSH, free T4
Hepatitis screening	HBV surface antigen (HBsAg), HCV viral load (RNA quant)
Urine	Microscopic Urinalysis

7.6 *Pregnancy Testing*

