4.1 Thyroid	
4.1.1 Primary hypothyroidism	
Definition: Elevated TSH, normal or low FT4	
Diagnostic work-up	
TSH and FT4 every 4-6 weeks as part of routine clinical monitoring on therapy or for case detection in symptomatic patients	
Grading	Management
G1: TSH < 10 mIU/L and asymptomatic G2: Moderate symptoms; able to perform ADL; TSH persistently > 10 mIU/L	Should continue ICPI with close follow-up and monitoring of TSH, FT4 May hold ICPI until symptoms resolve to baseline Consider endocrine consultation Prescribe thyroid hormone supplementation in symptomatic patients with any degree of TSH elevation or in asymptomatic patients with TSH levels that persist > 10 mIU/L (measured 4 weeks apart) Monitor TSH every 6-8 weeks while titrating hormone replacement to normal TSH FT4 can be used in the short term (2 weeks) to ensure adequacy of therapy in those with frank hypothyroidism where the FT4 was initially low Once adequately treated, should monitor thyroid function (at least TSH) every 6 weeks while on active ICPI therapy or as needed for symptoms to ensure appropriate replacement; repeat testing annually or as indicated by symptoms once stable
G3-4: Severe symptoms, medically significant or life-threatening consequences, unable to perform ADL	Hold ICPI until symptoms resolve to baseline with appropriate supplementation Endocrine consultation May admit for IV therapy if signs of myxedema (bradycardia, hypothermia) Thyroid supplementation and reassessment as in G2
Additional considerations For patients without risk factors, full replacement can be estimated with an ideal body weight–based dose of approximately 1.6 µg/kg/d For elderly or fragile patients with multiple comorbidities, consider titrating up from low dose, starting at 25-50 µg Extreme elevations of TSH can be seen in the recovery phase of thyroiditis and can be watched in asymptomatic patients to determine whether there is recovery to normal within 3-4 weeks Under guidance of endocrinology, consider tapering hormone replacement and retesting in patients with a history of thyroiditis (initial thyrotoxic phase) Adrenal dysfunction, if present, must always be replaced before thyroid hormone therapy is initiated	

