4.1.2 Hyperthyroidism	
Definition: Suppressed TSH and high normal or elevated FT4 and/or triiodothyronine	
Diagnostic work-up	
Monitor TSH, FT4 every 4-6 weeks from the start of therapy or as needed for case detection in symptomatic patients Consider TSH receptor antibodies if there are clinical features and suspicion of Grave disease (eg, ophthalmopathy) Close monitoring of thyroid function every 2-3 weeks after diagnosis to catch transition to hypothyroidism in patients with thyroiditis and hyperthyroidism	
Grading	Management
G1: Asymptomatic or mild symptoms	Can continue ICPI with close follow-up and monitoring of TSH, FT4 every 2-3 weeks until it is clear whether there will be persistent hyperthyroidism (see below) or hypothyroidism (see 4.1.1)
G2: Moderate symptoms, able to perform ADL	Consider holding ICPI until symptoms return to baseline Consider endocrine consultation β-Blocker (eg, atenolol, propranolol) for symptomatic relief Hydration and supportive care Corticosteroids are not usually required to shorten duration For persistent hyperthyroidism (> 6 weeks) or clinical suspicion, work-up for Graves disease (TSl or TRAb) and consider thionamide (methimazole or PTU) Refer to endocrinology for Graves disease
(continued on following page)	

Table 4. Management of Endocrine irAEs in Patients Treated With ICPIs (continued)	

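### Routine on-treatment TSH/T4 runs every 8 weeks in Tables 8 and 9, sparser than the 4-6 weeks in the Appendix 1 guideline; testing at Day 1 of every cycle from Cycle 2 would bring it to about 4 weeks on an existing blood draw

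*Combined protocol and SAP*

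**What the plan says.** Section 7.5 hands laboratory timing to the schedule tables: "Blood sampling will be performed for the following laboratory evaluations" follow Tables 8 and 9, and the text gives no separate thyroid schedule.

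- **Table 8 (Cohort A).** The row "endocrine (TSH, T4) (Section 7) Labs can be collected up to -3 days prior to treatment" is marked at screening, in the 8-weekly column (Day 1 of odd cycles) and at end of treatment (EOT).
- **Table 9 (Cohort B).** The same marks, plus one at post-operative Cycle 1 Day 1.
- **Table 10.** One further "endocrine (TSH, T4) (Section 7" test at the 30-day safety visit.
- **Other bloods.** The row "non-endocrine (CBC, CMP, Mag, Phos, LDH" is already marked at Cycle 2 Day 1 and on Day 1 of every later cycle in both tables.

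Appendix 1 is denser. Item 4.1.1 (hypothyroidism) has "TSH and FT4 every 4-6 weeks as part of routine clinical monitoring on therapy or for case detection in symptomatic patients". Item 4.1.2 (hyperthyroidism) has "Monitor TSH, FT4 every 4-6 weeks from the start of therapy or as needed for case detection in symptomatic patients". Once a subject is on replacement, the advice is that clinicians "should monitor thyroid function (at least TSH) every 6 weeks while on active ICPI therapy or as needed for symptoms". Section 5.8.1 presents Appendix 1 "with specific application to this protocol", and the Appendix header defines the checkpoint inhibitor as both study drugs.

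**The concern.** The schedule that governs blood sampling tests thyroid function less often than the guideline the protocol reproduces and applies to itself, and nothing explains the difference.

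Thyroid dysfunction is a documented event with these agents. Table 2 reports hypothyroidism in 16/199 and hyperthyroidism in 14/199 on INCMGA00012 alone, regardless of attribution. Section 1.3.1.2 names hyperthyroidism among the serious events judged at least possibly related to that drug in the flat-dose cohorts. Section 1.3.2.2 records Grade 2 hyperthyroidism as part of one dose-limiting toxicity with INCAGN01876 300 mg plus nivolumab.

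Subjects with recognised symptoms can be tested off schedule. The point therefore concerns subjects whose dysfunction is silent or is put down to something else. Misattribution is plausible here: the endocrine warning signs in Appendix 1 (headache, visual change, tiredness or weakness, altered mood or behaviour) overlap with the headache and neurologic deficit that Section 5.8.3 lists for cerebral edema.

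What is at stake is timeliness of detection only. The primary analysis is unaffected. The run-in rule is not materially affected either, because Section 5.7 exempts endocrinopathy controlled by hormone replacement.

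**Working it through.** **Interval as scheduled.** Cycles are 28 days, so Day 1 of cycle c falls on study day 28(c − 1) + 1. Odd cycles from Cycle 3 give days 57, 113, 169, …, a spacing of 56 days = 8.0 weeks, which reproduces the tables' 8-weekly column. With ±2-day visit windows at both ends the gap is 52 to 60 days. Adding the 3-day laboratory allowance gives 49 to 63 days. Even 49 days (7.0 weeks) exceeds the guideline's upper limit of 42 days.

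**Interval if every cycle from Cycle 2 is marked.** Days 29, 57, 85, 113, …, a spacing of 28 days (24 to 32 with visit windows; 21 to 35 with the laboratory allowance), all below 42.

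**First on-treatment test, Cohort A.** It moves from Day 57 to Day 29. Screening bloods may be up to 7 days before the first dose and the visit up to 2 days late. The longest gap from screening bloods therefore falls from 56 + 7 + 2 = 65 days to 28 + 7 + 2 = 37 days.

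**Detection delay.** Assume onset is uniform over a 56-day interval and ignore windows.
- Onset in days 1-28: found at day 56 instead of day 28, so 28 days later.
- Onset in days 29-56: found at day 56 either way, so no difference.
- Mean excess over testing every cycle: 0.5 × 28 = 14 days.
- Mean delay is interval/2: 28, 21 and 14 days for 8-, 6- and 4-week testing. The mean excess over a 6-week interval is 28 − 21 = 7 days.

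**Subjects affected, from Table 2 rates.** 16/199 = 8.0% and 14/199 = 7.0%. The combined rate is not given; it lies between 8.0% (full overlap) and 30/199 = 15.1% (no overlap).

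| | of 16 | of 32 |
|---|---|---|
| Cases (8.0% to 15.1%) | 1.29 to 2.41 | 2.57 to 4.82 |
| Low: × 0.5 × 25% without recognised symptoms | 0.16 | 0.32 |
| High: × 0.5 × 100% without recognised symptoms | 1.21 | 2.41 |

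The 25% to 100% share is an assumption; the documents give no figure.

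**Check against combination data.** Table 6 (INCAGN01876 plus nivolumab, N = 86) lists events above 5% and has no thyroid term. Since 5% of 86 is 4.3, each term occurred in at most 4/86 = 4.65%. At those ceilings the number found 28 days later, of 16, is at most 2 × 0.0465 × 16 × 0.5 = 0.74 (no overlap, all silent). With full overlap and 25% silent it is 0.0465 × 16 × 0.5 × 0.25 = 0.09. Hyperthyroidism as part of a dose-limiting toxicity was 1/56 = 1.8%.

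**Assays added.** 104 weeks / 4 = 26 cycles. The even cycles 2 to 26 number 13. Recurring tests rise from 12 to 25 per subject: 13 × 16 = 208 extra, or 13 × 32 = 416.

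**The case against.** The strongest case is that this is a defensible choice, not an error. Appendix 1 is a published guideline copied for convenience. Section 5.8.1 describes it as guidance on managing toxicities and delaying doses, while Section 7.5 gives sampling times to the tables. The thyroid entries also offer testing of symptomatic patients as an alternative. Subjects are seen every two weeks, with vital signs and adverse-event questioning, and Section 6.1 allows unscheduled visits. For silent, mild abnormalities Appendix 1 mostly continues treatment with closer follow-up, so earlier detection may change little. The numbers are small and rest on monotherapy rates. The delay model also ignores the EOT and 30-day tests.

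Much of this stands. No mandatory rule is breached, the benefit is modest, and the monotherapy-based counts may be too high. Two things remain. The guideline's wording covers routine monitoring on therapy as well as symptomatic testing, so the alternative does not make 8 weeks equal to 4-6. And symptom-led testing does not reach subjects whose symptoms are absent or misattributed.

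It is also true that the change below leaves one long gap in Cohort B, from the neoadjuvant dose to post-operative Cycle 1 Day 1. That gap can reach 14 + 35 = 49 days in sub-arm 2. In sub-arm 1 it can reach about 7 + 2 + 14 + 35 = 58 days with consecutive-day fractions, or 60 with the permitted every-other-day fractions.

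**Conclusion.** The point holds as an unreconciled inconsistency between the schedule tables and the guideline the protocol applies. Recurring thyroid tests are 56 days apart, against 28 to 42 in Appendix 1, and no permitted visit window closes the difference.

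The effect is small and confined to safety surveillance: a mean 14 days' later detection than with testing every cycle (7 days against a 6-week interval), assuming uniform onset. About 0.2 to 1.2 of 16 subjects, or 0.3 to 2.4 of 32, would be found 28 days later on monotherapy rates and the assumed silent share. The ceilings implied by Table 6 give 0.09 to 0.74 of 16. It does not threaten the trial's validity; it is worth correcting because the correction is cheap.

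**What to change.** In the endocrine row of Tables 8 and 9, mark TSH/free T4 at Cycle 2 Day 1 (W5) and in the 4-weekly Cycle X Day 1 column, drawn with the existing CBC/CMP sample under the same 3-day allowance. Keep the screening, EOT, 30-day safety visit and (Table 9) post-operative Cycle 1 Day 1 tests. The 8-weekly mark then becomes redundant.

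The cost is a schedule-table edit and at most 13 extra assays per subject over two years (208 for 16 subjects, 416 for 32), with no extra visit or needle stick. The downside is some repeat testing for mild incidental TSH shifts. The edit does not shorten Cohort B's single neoadjuvant-to-post-operative interval.
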